2. STATISTICAL HYPOTHESES

The null hypothesis of no difference in investigator-assessed DFS between the two treatment arms in the ITT population will be tested using the stratified log-rank test with type I error as 0.05. The null and alternative hypotheses in terms of the investigator-assessed DFS functions $S_{DFS_A}(t)$ and $S_{DFS_B}(t)$ in Arm A (atezolizumab) and Arm B (placebo) are phrased as below, respectively:

$$H_0: S_{DFS_A}(t) = S_{DFS_B}(t) \text{ versus } H_1: S_{DFS_A}(t) \neq S_{DFS_B}(t)$$

If statistical significance is achieved in investigator-assessed DFS, then the null hypothesis of no difference in overall survival (OS) between the two arms in the ITT population will be tested using the stratified log-rank test with the allocated type I error at the interim and final analyses (Section 3.1). The null and alternative hypotheses in terms of the survival functions $S_{OS_A}(t)$ and $S_{OS_B}(t)$ in Arm A and Arm B are phrased as below, respectively:

$$H_0: S_{OS_A}(t) = S_{OS_B}(t) \text{ versus } H_1: S_{OS_A}(t) \neq S_{OS_B}(t)$$

3. SAMPLE SIZE DETERMINATION

3.1 TYPE I ERROR CONTROL

Type I error rate for this study is 0.05 (two-sided). To control the type I error rate at $\alpha = 0.05$ (two-sided) for the primary endpoint of investigator-assessed DFS and the key secondary endpoint of OS, the treatment arms will be compared in a hierarchical fashion. The analysis hierarchy will be investigator-assessed DFS followed by OS. One planned analysis of investigator-assessed DFS and a total of three planned analyses of OS (two interim analyses and one final analysis; see Section 5.8 for details) will be performed by the Sponsor. The analysis hierarchy will be implemented as follows:

Step 1: Investigator-assessed DFS will be evaluated at $\alpha = 0.05$ (two-sided). The final analysis will be conducted when approximately 334 DFS events (44% of

764 patients) have occurred. The investigator-assessed DFS endpoint will be considered positive in the ITT population if statistical significance is achieved at the DFS final analysis.

Step 2: If the investigator-assessed DFS results are statistically significant at the DFS final analysis, $\alpha = 0.05$ will be passed to the analysis of OS. At the time of the investigator-assessed DFS final analysis, the first OS interim analysis will be performed and it is projected that approximately 190 deaths will have occurred (25% of 764 patients). The second interim, and final analyses of OS will be conducted when approximately 222, and 254 deaths (29%, and 33% of 764 patients) have occurred, respectively. For control of the familywise error rate at level 0.05, OS will be evaluated on the basis of the generalized Haybittle–Peto boundary ([Haybittle 1971](#)) for statistical significance, with alpha boundaries for the two interim and final analyses specified as the following: 0.036, 0.036, and 0.011. Specifically, if at the DFS final analysis, the observed number of OS events is significantly less than the projected 190 events (e.g., < 170 events), a nominal alpha value ($1E-05$) will be spent at the first OS interim analysis and the team will conduct an additional interim analysis of OS when 190 events have occurred. If the investigator-assessed DFS results are not statistically significant at the DFS final analysis, formal treatment comparison of OS will not be performed.

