6.10 INTERIM ANALYSES

6.10.1 Planned Interim Analyses

There is no planned interim efficacy analysis of the primary endpoint of *investigator-assessed* DFS for this study. A total of three analyses of OS will be performed (two interim analyses and one final analysis). OS will be evaluated on the basis of the generalized Haybittle-Peto boundary (Haybittle 1971) for statistical significance, with p-value *boundaries* at each interim or final analysis specified as the following: 0.036, 0.036, and 0.011.

The first interim analysis of OS will be performed at the time of the *investigator-assessed* DFS analysis (projected to occur at Month 67 after the first patient is randomized), if DFS is statistically significant. On the basis of the projected median OS for each treatment arm, the projected number of deaths observed at the DFS

analysis is approximately 190 deaths (25% of 764 patients), which corresponds to approximately 75% of the number of deaths required for the final analysis of OS. The observed HR of OS that is projected to result in a statistically significant difference between treatment arms at the DFS analysis is less than or equal to 0.73.

The second interim analysis of OS will be performed when approximately 222 deaths have occurred (29% of 764 patients), corresponding to approximately 87.5% of the number of deaths required for the final analysis of OS. The required number of OS events for the second interim analysis of OS is projected to occur at Month 77. The observed HR that is projected to result in a statistically significant difference between treatment arms at this analysis is OS HR 0.75 or lower.

The boundary for statistical significance at the OS interim and final analyses will be adjusted based on the actual number of events observed. Specifically, if at the DFS analysis, the observed number of OS events is significantly less than the projected 190 events, a nominal alpha value ($1E-05$) will be spent at the first OS interim analysis and the team will conduct another interim analysis of OS when 190 events have occurred.

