3.2 INVESTIGATOR-ASSESSED DISEASE-FREE SURVIVAL

The final analysis of the primary endpoint of investigator-assessed DFS will take place when approximately 334 DFS events have occurred (44% of 764 patients) on the basis of the following assumptions:

- Log-rank test (two-sided)
- Type I error rate (α) of 0.05 (two-sided)
- 1:1 randomization ratio
- 5% loss to follow-up over 24 months
- Median DFS for the control (placebo) arm of 47 months and estimated median DFS in the atezolizumab arm of 67 months (corresponding to a hazard ratio (HR) of 0.70, under the proportional hazard assumption)
- 90% power

Accrual of the planned 764 patients is projected to occur over 33 months, assuming a ramp-up period of 8 months. On the basis of these assumptions, the required number of DFS events for final analysis is projected to occur at Month 67 after the first patient is randomized; minimum follow-up at the time of the investigator-assessed DFS final analysis will be 34 months. Also on the basis of these assumptions, it is projected that an observed HR of ≤ 0.80 at the final analysis will result in a statistically significant difference (i.e., minimally detectable difference) between treatment arms. An HR of 0.80 corresponds to an improvement of 12 months in median DFS, from 47 months in the control (placebo) arm to 59 months in the atezolizumab arm.

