3.3 OVERALL SURVIVAL

The final analysis of the secondary endpoint of OS will take place when approximately 254 deaths have occurred (33% of 764 patients), on the basis of the following assumptions:

- Log-rank test (two-sided)
- Type I error rate (alpha) of 0.05 (two-sided)
- 1:1 randomization ratio
- 2% loss to follow-up over 24 months for OS
- Two interim analyses for OS will take place when approximately 190 and 222 deaths have occurred, respectively
- Alpha boundary is set to be 0.036, 0.036, and 0.011 for the three analyses of OS based on the generalized Haybittle-Peto boundary
- Median OS for the control (placebo) arm of 100 months and estimated median OS in the atezolizumab arm of 143 months (corresponding to HR of 0.70)
- 75% power

On the basis of these assumptions and projected accrual, the required number of OS events for the final analysis of OS is projected to occur at Month 88 from the time the first patient is randomized. Also on the basis of these assumptions, it is projected that an observed HR of ≤ 0.73 and 0.75 at the first and second interim analyses, and an HR of ≤ 0.72 at the final analysis of OS, respectively, will result in a statistically significant difference (i.e., minimally detectable difference) between treatment arms.

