5.8 INTERIM ANALYSES

5.8.1 Planned Interim Analyses

There is no planned interim efficacy analysis of the primary endpoint of investigator-assessed DFS for this study. A total of three analyses of OS are planned (two interim analyses and one final analysis). OS will be evaluated on the basis of the generalized Haybittle-Peto boundary (Haybittle 1971) for statistical significance, with p-value boundaries at each interim or final analysis specified as the following: 0.036, 0.036, and 0.011.

The first interim analysis of OS will be performed at the time of the investigator–assessed DFS final analysis (projected to occur at Month 67 after the first patient is randomized), if DFS is statistically significant at the final analysis. On the basis of the projected median OS for each treatment arm, the projected number of deaths observed at the DFS final analysis is approximately 190 deaths (25% of 764 patients), which corresponds to approximately 75% of the number of deaths required for the final analysis of OS. The observed HR of OS that is projected to result in a statistically significant difference between treatment arms at the DFS final analysis is less than or equal to 0.73.

The second interim analysis of OS will be performed when approximately 222 deaths have occurred (29% of 764 patients), corresponding to approximately 87.5% of the number of deaths required for the final analysis of OS. The required number of OS events for the second interim analysis of OS is projected to occur at Month 77. The observed HR that is projected to result in a statistically significant difference between treatment arms at this analysis is OS HR 0.75 or lower.

The boundary for statistical significance at the OS interim and final analyses will be adjusted based on the actual number of events observed. Specifically, if at the DFS final analysis, the observed number of OS events is significantly less than the projected 190 events (e.g., < 170 events), a nominal alpha value (1E–05) will be spent at the first OS interim analysis and the team will conduct an additional interim analysis of OS when 190 events have occurred.

Table 2 Projected Interim and Final OS Analysis Characteristics

Analysis	No. of events	% information	Event to Patient Ratio	Projected Cutoff Date^a	Projected MDD^b	Projected Boundary (p-value)^c
First interim	190	75%	25%	Month 67	0.73	p ≤0.036
Second interim	222	87.5%	29%	Month 77	0.75	p ≤0.036
Final	254	100%	33%	Month 88	0.72	p ≤0.011

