MDD= minimally detectable difference; OS=overall survival.

Note: Assumes 2% dropout rate over 24 months for OS analyses.

^a Study month at which required number of events are projected to occur, where Study Month 1 is the month the first patient is enrolled.

^b The largest observed hazard ratio that is projected to be statistically significant.

^c The projected boundary for statistical significance for the number of events shown (actual boundary to be calculated at time of analysis based on actual number of events).

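### Are the OS boundaries left undefined because only a shortfall of deaths at the first look is written out?

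*SAP*

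**What the plan says.** SAP 3.1 and 5.8.1 set three OS analyses at about 190, 222 and 254 deaths, with two-sided p-limits 0.036, 0.036 and 0.011 on a generalized Haybittle-Peto boundary and a familywise level of 0.05. The first look coincides with the DFS final analysis (334 events), so its death count is a projection: "On the basis of the projected median OS for each treatment arm, the projected number of deaths observed at the DFS final analysis" is about 190, resting on "Median OS for the control (placebo) arm of 100 months and estimated median OS in the atezolizumab arm of 143 months". The second is timed by deaths: "The second interim analysis of OS will be performed when approximately 222 deaths have occurred (29% of 764 patients".

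On departures from projection, SAP 5.8.1 states: "The boundary for statistical significance at the OS interim and final analyses will be adjusted based on the actual number of events observed". Note c to SAP Table 2 says the same: "actual boundary to be calculated at time of analysis based on actual number of events". The one worked case is a shortfall. In SAP 3.1 it applies when "the observed number of OS events is significantly less than the projected 190 events (e.g., < 170 events"; Protocol 6.10.1 gives no number: "the observed number of OS events is significantly less than the projected 190 events, a nominal alpha value". In that case 1E-05 is spent at the first look and a further look is added at 190 deaths. No recalculation method is named, and nothing says what becomes of the second look if 222 deaths have already occurred.

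**The concern.** OS is tested only if DFS is significant, so the OS error rate matters most when DFS works and OS does not. The death rate in the active arm is then higher than projected, and the DFS trigger arrives with more than 190 deaths. The first look can land next to the second, or beyond it, and that is the direction with no worked case.

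Fixing the total at 0.05 does not by itself fix the final limit, because several valid recalculations share that total. A final HR of 0.75 could succeed under one and fail under another. Under SAP 1.2.2 the sponsor is blinded only until the primary analysis, which is also the first OS look. If the method were still open then, it could in principle be chosen with OS results in view.

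**Working it through.** **Inputs.** Deaths 190/222/254, p-limits 0.036/0.036/0.011, 75% power, OS medians 100/143 months, 2% loss per 24 months (SAP 3.1, 3.3, 5.8.1). "Median DFS for the control (placebo) arm of 47 months and estimated median DFS in the atezolizumab arm of 67 months", 334 events, 5% loss per 24 months, 764 patients over 33 months with an 8-month ramp (SAP 3.2). The 100-month median in both arms is the assumption for no OS effect.

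**Step 1: reproduce the plan.** The log-rank Z statistics at d₁, d₂, d₃ deaths are treated as normal with correlation √(dᵢ/dⱼ). The limits correspond to |Z| > 2.097, 2.097 and 2.543. Recursive integration at 190/222/254 gives a total of 0.0501, which is 0.05 within rounding: interims at 0.0359 with a final of 0.011 give 0.0500, cumulatively 0.0359, 0.0492, 0.0500. Power at HR 0.70 is 75.4%. The HR limit is exp(−2z/√d):

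- 190 deaths: exp(−2 × 2.097/√190) = 0.738
- 222 deaths: 0.755
- 254 deaths: exp(−2 × 2.543/√254) = 0.727

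The plan prints 0.73, 0.75 and 0.72, the same values truncated. With uniform accrual, expected deaths are 191 at Month 67, 222 at Month 77 and 253 at Month 88. The planned design is sound.

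**Step 2: deaths at the 334th DFS event.** Simulation with exponential times and DFS HR 0.70 (0.80 in the fourth row), taking DFS and OS from independent to fully dependent:

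| OS assumption | Mean deaths | P(222 or more) |
|---|---|---|
| HR 0.70 (plan) | 189 | 0–2% |
| HR 0.84 | 203 | 2–12% |
| HR 0.90 | 208 | 8–19% |
| HR 1.0, DFS HR 0.80 | 206 | 5–18% |
| HR 1.0, medians 110/110 | 200 | 1–9% |
| HR 1.0, medians 100/100 | 217 | about 30–40% |

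In the last row fewer than 170 deaths occur in at most 0.2% of trials.

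**Step 3: recalculate at 217/222/254**, each solved to total 0.0500:

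| Rule | p-limits (first/second/final) | Final HR limit |
|---|---|---|
| Planned cumulative alpha kept by look | 0.0359/0.0473/0.0127 | 0.732 |
| Interims held, final solved | 0.0359/0.0359/0.0319 | 0.764 |
| Second look dropped | 0.0359/none/0.0369 | 0.770 |
| Spending interpolated linearly in deaths | 0.0471/0.0364/0.0120 | 0.730 |

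The spread is real. Every row controls the error.

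**Step 4: is there inflation?** The printed limits left unchanged at 217/222/254 total 0.0421, which is conservative. Unchanged at 170/222/254 they would total 0.0538, so recalculation is needed there. It is promised, and the choices are close: 0.0359/0.0306/0.0099 by look, against equal interims of 0.0332 with a final of 0.011. Below 170 the written rule (1E-05, then 190/222/254) totals 0.0501, as planned. Inflation at 217 appears only if the rule is picked after results: up to 0.0548 if chosen after the first look, or 0.0561 if left open until after the second.

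**Step 5: would an explicit excess rule help?** Take a cutoff midway between 190 and 222, dropping the second look at 206 or more deaths and otherwise keeping cumulative alpha by look. At 205 deaths the final limit is 0.0120 (HR 0.730); at 206 it is 0.0342 (HR 0.767). One death moves the HR limit by 0.037, about as much as the 0.730–0.770 spread it was meant to remove. The DFS trigger is only approximately 334 events, so a small shift in cutoff date could cross that line. A three-look cumulative schedule starting at 0.0359 also does not fit the shortfall rule, which has four looks and starts at 1E-05.

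**The case for a change.** The best case for a change is that the written rule covers the direction that almost never occurs when OS shows no effect, and is silent on the one that often does. At 217 deaths a final HR of 0.75 succeeds under two of the four recalculations and fails under the other two. The sponsor performs these analyses and loses its blind at the first of them. Protocol 6.10.2 asks more of an optional interim: its type I error control must be in the SAP and with health authorities at least two months ahead. Naming a method would cost a few sentences.

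Part of this stands. No method is named, and the fate of the second look is unstated if 222 deaths have passed.

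The rest is weaker. The adjustment sentence is not limited to shortfalls. Dropping the second look at 217 deaths goes against a plan that schedules three analyses, and the linear interpolation appears nowhere in the documents. Without those two, the final limit runs from 0.013 to 0.032. The closest reading of a Haybittle-Peto boundary with equal interim limits is to hold the interims and solve the final, although SAP 5.8.1 says interim boundaries are adjusted too, so that reading is not certain. The documents tie the recalculation to event counts, and the pooled death count can be known without treatment codes.

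**Conclusion.** No change to the plan follows. The total is fixed at 0.05, recalculation to actual deaths is promised in both directions, and any single count-based method meets that promise. What is absent is the method's name, which the study statistician would settle from the pooled death count as part of ordinary preparation for the DFS analysis. No stated rule inflates type I error. The figures of 0.0548 and 0.0561 describe a choice made on OS results, which the plan does not permit or imply.

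The spread in the final limit (0.013 to 0.032 with three looks kept, 0.037 with one dropped) is largest in a narrow setting: DFS HR 0.70, OS HR 1.0 and a 100-month control median. Under the plan's OS HR of 0.70 the first look averages 189 deaths and reaches 222 in 0–2% of trials. Whether to keep or drop a second look that falls close to the first is a fair trade-off between an extra look and a more generous final limit, and a hard cutoff for it brings its own discontinuity. These results assume exponential event times and the plan's accrual and loss rates.

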3.2 INVESTIGATOR-ASSESSED DISEASE-FREE SURVIVAL

The final analysis of the primary endpoint of investigator-assessed DFS will take place when approximately 334 DFS events have occurred (44% of 764 patients) on the basis of the following assumptions:

- Log-rank test (two-sided)
- Type I error rate (α) of 0.05 (two-sided)
- 1:1 randomization ratio
- 5% loss to follow-up over 24 months
- Median DFS for the control (placebo) arm of 47 months and estimated median DFS in the atezolizumab arm of 67 months (corresponding to a hazard ratio (HR) of 0.70, under the proportional hazard assumption)
- 90% power

Accrual of the planned 764 patients is projected to occur over 33 months, assuming a ramp-up period of 8 months. On the basis of these assumptions, the required number of DFS events for final analysis is projected to occur at Month 67 after the first patient is randomized; minimum follow-up at the time of the investigator-assessed DFS final analysis will be 34 months. Also on the basis of these assumptions, it is projected that an observed HR of ≤ 0.80 at the final analysis will result in a statistically significant difference (i.e., minimally detectable difference) between treatment arms. An HR of 0.80 corresponds to an improvement of 12 months in median DFS, from 47 months in the control (placebo) arm to 59 months in the atezolizumab arm.

3.3 OVERALL SURVIVAL

The final analysis of the secondary endpoint of OS will take place when approximately 254 deaths have occurred (33% of 764 patients), on the basis of the following assumptions:

- Log-rank test (two-sided)
- Type I error rate (alpha) of 0.05 (two-sided)
- 1:1 randomization ratio
- 2% loss to follow-up over 24 months for OS
- Two interim analyses for OS will take place when approximately 190 and 222 deaths have occurred, respectively
- Alpha boundary is set to be 0.036, 0.036, and 0.011 for the three analyses of OS based on the generalized Haybittle-Peto boundary
- Median OS for the control (placebo) arm of 100 months and estimated median OS in the atezolizumab arm of 143 months (corresponding to HR of 0.70)
- 75% power

On the basis of these assumptions and projected accrual, the required number of OS events for the final analysis of OS is projected to occur at Month 88 from the time the first patient is randomized. Also on the basis of these assumptions, it is projected that an observed HR of ≤ 0.73 and 0.75 at the first and second interim analyses, and an HR of ≤ 0.72 at the final analysis of OS, respectively, will result in a statistically significant difference (i.e., minimally detectable difference) between treatment arms.

4. ANALYSIS SETS

The following populations are defined:

Population	Definition
ITT	All randomized patients regardless of whether the assigned study treatment was received.
Safety-evaluable	All randomized patients who received any amount of study treatment (i.e., atezolizumab or placebo), regardless of whether a full or partial dose was received. Specifically, for patients randomized to the placebo arm, if atezolizumab was received by mistake, patients will be grouped under the atezolizumab arm in the safety analyses.
PRO-Evaluable	All randomized patients with a non-missing baseline PRO assessment and at least one post-baseline assessment. The PRO-evaluable population will be defined for each questionnaire (i.e., the FKSI-19 evaluable population and the EQ-5D-5L evaluable population).
Immunogenicity Analysis	All randomized patients with at least one ADA assessment for atezolizumab
Post-baseline ADA-Evaluable	All randomized patients who received at least one dose of atezolizumab and with at least one postdose ADA assessment
Pharmacokinetic-Evaluable	All randomized patients who received any dose of study treatment and who have at least one measurable post-baseline PK sample available

ADA = anti-drug antibody; EQ-5D-5L = EuroQoL 5-Dimension, 5-level version;
FKSI-19 = Functional Assessment of Cancer Therapy Kidney Symptom Index 19;
ITT = intent-to-treat; PK=pharmacokinetic; PRO = patient reported outcomes.

5. STATISTICAL ANALYSES

5.1 GENERAL CONSIDERATIONS

All efficacy analyses will be performed in the ITT population, unless otherwise specified. Patients will be analyzed according to the treatment assigned at randomization by IxRS.

All IRF-assessed DFS and EFS analyses will use the tumor assessments per the revised charter ([2nd Stream](#)), unless otherwise specified in the sensitivity analyses (Section [5.4.3.1](#)).

All safety analyses will be performed in the safety-evaluable population, unless otherwise specified. Patients will be analyzed according to the treatment they actually received.

